6.2. Effectiveness Endpoints

Not applicable.

6.3. Other Endpoints

Not applicable.

6.4. Covariates

No covariates have been identified for the safety or effectiveness of this product on the basis of currently available data including those from clinical studies.

7. HANDLING OF MISSING DATA

If the seriousness of an adverse event, action taken for an adverse event, or outcome of an adverse event is missing, the event will be treated as having a value of "unknown" for data tabulation. If the causality of an adverse event is missing, the event will be treated as "causally related" for data tabulation.

Cleaning-uncompleted data will be in principle handled as follows:

- Items for which relevant data are missing: For both tabulation and listing, their values will be handled as missing data (or they will be treated as "unknown" for a categorical variable).
- Items for which relevant data are inconsistent: For both tabulation and listing, their values will be handled as missing data. In addition, a list will be presented separately for details of data-handling.
- Items with no signature: For both tabulation and listing, any record in a CRF with no signature of a contract physician (including when the CRF is signed only by individuals other than contract physicians) will be handled as missing data.

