8.2.3. Safety analyses

The listings will include all relevant events reported in this study.

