8.2.3.1.3. Details of adverse reactions

Adverse reactions will be summarized by SOC and PT in terms of n and proportion by each of the following factors:

- Seriousness [serious, non-serious]
- Action taken (additional treatment) [present, absent]
- Outcome [death, not resolved, resolved with sequelae, resolving, resolved/recovered, unknown]

- Severity [life-threatening, severe, moderate, mild]

Participants who experienced multiple adverse reactions with the same PT will be summarized in the manner described below in terms of summarization of n:

- Seriousness: If there are both serious and non-serious events, they are regarded as serious.
- Days to onset: The days to the first onset will be adopted.
- Action taken (additional treatment): If multiple actions were taken for adverse reactions occurring in the same participant with the same PT, only one kind of action will be adopted with “present” being given priority over “absent.”
- Outcome: The outcome for the last reaction will be adopted.
- Severity: For a participant experiencing multiple adverse reactions with the same PT in different severities, the participant will be handled as having experienced an event of one level of severity with “life-threatening,” “severe,” “moderate,” and “mild” being given priority in this order.

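### For data still uncleaned at the cut-off, SAP 7 turns a contradictory seriousness entry into an unknown value, which drops out of the serious-event counts and has no row in the adverse event tables

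*SAP*

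**What the plan says.** SAP 7 gives default values for missing adverse event items. Missing seriousness, action taken or outcome is tabulated as unknown. Causality is treated differently: "If the causality of an adverse event is missing, the event will be treated as" causally related.

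A second set of rules opens with "Cleaning-uncompleted data will be in principle handled as follows". Its second bullet reads "Items for which relevant data are inconsistent: For both tabulation and listing, their values will be handled as missing data", and continues: "In addition, a list will be presented separately for details of data-handling". No exception is made for seriousness or severity.

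The tables that use seriousness are:

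- SAP 8.2.3.1.2: serious adverse reactions.
- SAP 8.2.3.1.3: details of adverse reactions, with seriousness split into serious and non-serious only. Several reactions with the same preferred term in one child are combined by this rule: "If there are both serious and non-serious events, they are regarded as serious".
- SAP 8.2.3.2.1 and 8.2.3.2.2: serious and non-serious adverse events. No table of all adverse events is planned.

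SAP 9 plans one listing of participants with adverse events and a separate one of those with serious adverse events. SAP 8.2.3 adds: "The listings will include all relevant events reported in this study".

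**The concern.** Suppose two fields of one event disagree about seriousness. For example, a seriousness criterion is ticked but the event is marked non-serious. The physician has recorded some evidence that the event was serious, and the blanking rule removes it from the tabulation. An inconsistent causality entry passes through the same rule and comes out as related, so the evidence for a reaction is kept. No reason is given for treating the two items differently.

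This is a single-arm, safety-only study with a target of 60 children, and its aim is to confirm early safety. In a group that small, the difference between one serious event and none can change the message of the table. The exposure is greatest at the regular J-PSUR interim analyses (SAP 3), where queries may still be open, and for any query left open at database release.

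**Working it through.** **The plan's own figure.** SAP 2.2.7 says that an event with 3% true incidence is seen at least once among 60 children with probability 83%. The check is 1 − 0.97^60 = 0.839, which agrees to within a point. This is background only; the point here concerns a data-handling rule.

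**Following one event through the rules.** Take an adverse event with contradictory seriousness entries and the query open at the cut-off.

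1. SAP 7, second bullet: the seriousness value is handled as missing, in tables and listings.
2. SAP 7, first sentence: missing seriousness is tabulated as unknown.
3. The event is then neither serious nor non-serious. The outputs treat it as follows.

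| Output | Depends on seriousness? | Result |
|---|---|---|
| All adverse reactions (8.2.3.1.1) | No | Counted if related or causality missing |
| Serious adverse reactions (8.2.3.1.2) | Yes | Not counted |
| Reaction details by seriousness (8.2.3.1.3) | Yes | No category for unknown |
| Serious adverse events (8.2.3.2.1) | Yes | Not counted |
| Non-serious adverse events (8.2.3.2.2) | Yes | Not non-serious either; no row stated |
| Listing of all adverse events (9) | No | Present, seriousness blank |
| Listing of serious adverse events (9) | Yes | Not stated; may be absent |
| Data-handling list (7) | No | The alteration is shown |

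An event judged unrelated does not reach the adverse reaction tables, so it appears in no adverse event table at all. In SAP 8.2.3.1.3 the outcome categories include unknown, but the seriousness categories do not.

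**Causality, for comparison.** Inconsistent causality becomes missing under the same bullet, and missing causality is tabulated as related. The event is kept in the reaction count.

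**Size, as an illustration.** Inputs: n = 60 (SAP 2.2.7) and the exact two-sided 95% interval (SAP 8.1.3). Assumptions: no other serious event, and x children with one such entry each. The documents do not give x; 1 to 3 is shown.

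- Under the present rule: 0/60. Upper limit = 1 − 0.025^(1/60) = 0.0596, so 0% to 6.0%.
- x = 1, counted as serious: 1/60 = 1.7%. Lower limit = 1 − 0.975^(1/60) = 0.0004. The upper limit solves (1 − p)^60 + 60p(1 − p)^59 = 0.025, giving p = 0.0894. Interval 0.04% to 8.9%.
- x = 2: 2/60 = 3.3% (0.4% to 11.5%).
- x = 3: 3/60 = 5.0% (1.0% to 13.9%).

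Each such child with no other serious event lowers the serious proportion by 1/60 = 1.7 percentage points.

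**The case against.** The strongest reply is that this is a disclosed choice with narrow reach. The rule covers only uncleaned data, and only in principle. Sites answer queries and correct the CRF (Protocol 8.6.5.2). About five months separate the end of data collection from database release (28 April to 24 September 2024, Protocol 5). Every serious adverse event also goes to the sponsor's safety group within 24 hours, whatever its causality (Protocol 10.1). All of this stands, and it limits how often the rule will bite. It does not correct the study tables when the rule does apply, and the 24-hour reports could then show a serious event that the tables lack.

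A reader might also infer more than the documents support:

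- *That the event disappears.* It does not. The rule acts on an item's value, not on the event, which stays in the listing of all adverse events and in the data-handling list.
- *That it certainly leaves the serious-event listing, against SAP 8.2.3.* The SAP does not say so. Blanking one field is compatible with listing all relevant events; what is unstated is whether an event with blank seriousness counts as relevant to that listing.
- *That every inconsistent safety item is resolved towards safety.* Causality goes the other way.
- *That the SAP breaks a general worst-case convention.* It has none. Missing outcome is unknown, and SAP 8.2.3.1.3 keeps the last outcome, not the worst. Its serious-first and worst-severity rules combine several reactions with the same preferred term; they neither resolve nor are breached by one contradictory entry.
- *That COVID-19 severity is equally exposed, for instance through onset absent with ICU admission present.* Protocol 8.3.7 asks for the actions taken only when onset is present, so the collection scheme works against that entry.

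The CRF layout is not in the documents. Protocol 8.3.8.2 has the investigator select a criterion for serious events, so how easily a contradictory seriousness entry can arise is unknown.

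**Conclusion.** The point holds for data still uncleaned at an analysis cut-off. Read together, the rules in SAP 7 remove an event with contradictory seriousness from the serious counts, and the planned tables give unknown seriousness no place. For an unrelated event, that means no adverse event table at all. The loss is in the tables; the listing of all adverse events and the data-handling list keep a trace, and the effect on the serious-event listing is a possibility the SAP leaves open.

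The size is one child in 60 per entry: 0% (0% to 6.0%) instead of 1.7% (0.04% to 8.9%) when it is the only serious event. This rests on the assumed number of entries and on there being no other serious event. With complete cleaning the effect is nil. The change is worth making because the study is about safety only, the rule discards recorded evidence of seriousness, and the remedy is small.

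**What to change.** Add to SAP 7: *An unresolved inconsistency in the seriousness or severity of an adverse event is tabulated at the worse of the recorded values. Listings show the values as recorded, with a flag.*

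Add an unknown row for events whose seriousness is wholly missing, in the seriousness breakdown of SAP 8.2.3.1.3 and alongside the serious and non-serious tables of SAP 8.2.3.2, so that every event has a place. Leave unchanged the last-outcome rule in SAP 8.2.3.1.3, the rule for other inconsistent items, and the separate data-handling list.

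The cost is a sentence or two in the SAP, a small programming rule and an extra row. The downside is that an interim table may over-count serious or severe events until a query is resolved downwards; the flag in the listing makes such events identifiable.

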8. STATISTICAL METHODS AND ANALYSIS

8.1. Statistical Methods

8.1.1. Continuous variables

For continuous variables, summary statistics (n, mean, standard deviation [SD], median, maximum, minimum) will be presented.

8.1.2. Categorical variables

For categorical variables, participants included in each category will be calculated in terms of frequency (such as n) and proportion.

8.1.3. Binary variables

For binary variables, participants included in each binary category will be calculated in terms of frequency and proportion. When a confidence interval (CI) is determined for a proportion, the two-sided 95% CI (exact method) will be determined.

8.2. Statistical Analyses

8.2.1. Participant description

8.2.1.1. Constitution

Among CRF-fixed participants, those included in the safety analysis set will be tabulated. In addition, participants excluded from the safety analysis set, and those excluded from the safety analysis set for each reason will be tabulated.

8.2.1.2. Discontinuation and dropouts

Using the safety analysis set, participants completing/discontinuing this study at the end of the observation period will be summarized in terms of n and proportion. Participants discontinuing this study will be summarized by reason of discontinuation for both n and proportion. Regarding the reason of discontinuation, a list will be prepared if other is selected.

8.2.1.3. Participants excluded from analysis

Participants excluded from the safety analysis set will be listed in a tabular form with their reasons for exclusion.

8.2.2. Vaccinated participant characteristics and treatment history

8.2.2.1. Vaccinated participant characteristics

Using the safety analysis set, characteristics of vaccinated participants will be summarized according to Section 8.1 with respect to the following factors:

- Sex [male, female]
- Age [6 months to <2 years, 2 years to ≤4 years]
- Hepatic impairment [absent, present]
- Renal impairment [absent, present]
- Medical history [absent, present]
- Complications [absent, present]
- Past history of allergy [absent, present]

- Types of initial immunization with COVID-19 vaccines (first dose, second dose, third dose)
[COMIRNATY (monovalent: Original), COMIRNATY (monovalent: XBB1.5), other]

Using the safety analysis set, a breakdown of participants according to each of the following factors will be presented in terms of n and proportion by system organ class (SOC) and preferred term (PT):

- Medical history
- Complications

8.2.2.2. Status of immunization with this product

Using the safety analysis set, the status of immunization with this product will be summarized with respect to the following:

- Dose interval between the initial immunization (third dose) and the fourth vaccination (continuous) (date of 4th dose – date of 3rd dose)
- Dose interval between the initial immunization (third dose) and the fourth vaccination [<3 months (<90 days), ≥ 3 months]
- Vaccination site [shoulder (deltoid muscle), lateral thigh, other]
- Inoculation dose [0.2 mL, other]

8.2.3. Safety analyses

The listings will include all relevant events reported in this study.

8.2.3.1. Adverse reactions

8.2.3.1.1. All adverse reactions

Adverse reactions will be summarized by SOC and PT in terms of n and proportion.

8.2.3.1.2. Serious adverse reactions

Serious adverse reactions will be summarized by SOC and PT in terms of n and proportion.

8.2.3.1.3. Details of adverse reactions

Adverse reactions will be summarized by SOC and PT in terms of n and proportion by each of the following factors:

- Seriousness [serious, non-serious]
- Action taken (additional treatment) [present, absent]
- Outcome [death, not resolved, resolved with sequelae, resolving, resolved/recovered, unknown]

- Severity [life-threatening, severe, moderate, mild]

Participants who experienced multiple adverse reactions with the same PT will be summarized in the manner described below in terms of summarization of n:

- Seriousness: If there are both serious and non-serious events, they are regarded as serious.
- Days to onset: The days to the first onset will be adopted.
- Action taken (additional treatment): If multiple actions were taken for adverse reactions occurring in the same participant with the same PT, only one kind of action will be adopted with “present” being given priority over “absent.”
- Outcome: The outcome for the last reaction will be adopted.
- Severity: For a participant experiencing multiple adverse reactions with the same PT in different severities, the participant will be handled as having experienced an event of one level of severity with “life-threatening,” “severe,” “moderate,” and “mild” being given priority in this order.

8.2.3.1.4. Safety specification

For the following elements in the safety specification, participants who experienced a relevant event will be listed in a tabular form:

- Shock, anaphylaxis

Definition: Any event coded as one of the following PTs:

Anaphylactic reaction, anaphylactic shock, anaphylactoid reaction, anaphylactoid shock

- Myocarditis, pericarditis

Definition: Any event corresponding to the following MedDRA SMQ (narrow):

Noninfectious myocarditis/pericarditis

- VAED and VAERD

Definition: Any event coded as either of the following LLTs:

Vaccine associated enhanced respiratory disease, vaccine associated enhanced disease

OR any event coded as one of the following PTs:

Abdominal pain, acute hepatic failure, acute kidney injury, acute myocardial infarction, acute respiratory distress syndrome, altered state of consciousness, arrhythmia, cardiac failure, cardiogenic shock, cerebrovascular accident, chillblains, COVID-19 pneumonia, deep vein thrombosis, diarrhoea, disseminated intravascular coagulation, dyspnoea, encephalopathy, erythema multiforme, hypoxia, jaundice, meningitis, multiple organ dysfunction syndrome, multisystem inflammatory syndrome in children, myocarditis, peripheral ischaemia, pulmonary embolism, renal failure, respiratory failure, seizure, shock, tachypnoea, thrombocytopenia, vasculitis, vomiting

- Guillain-Barre syndrome

Definition: Any event corresponding to the following MedDRA SMQ (narrow):

Guillain-Barre syndrome

8.2.3.1.5. Occurrence of adverse reactions in participants excluded from the safety analysis set

Using data from CRF-collected participants, adverse reactions reported in participants excluded from the safety analysis set will be identified and presented in a tabular form. The adverse reactions identified will also be summarized in terms of n by SOC and PT.

8.2.3.2. Adverse events

8.2.3.2.1. Serious adverse events

Serious adverse events will be summarized by SOC and PT in terms of n and proportion.

8.2.3.2.2. Non-serious adverse events

Non-serious adverse events will be summarized by SOC and PT in terms of n and proportion. In this tabulation, a threshold of incidence will be set as necessary, and only events with an incidence \geq the threshold will be summarized.

8.2.3.3. Reactogenicity events

The following reactogenicity events will be summarized:

- For vaccinated participants who are younger than 2 years of age at the time of the fourth vaccination with this product
 - Local reactions: injection site tenderness, redness, and injection site swelling
 - Systemic reactions: pyrexia, decreased appetite, somnolence, and irritability
- For vaccinated participants who are 2 years or older at the time of the fourth vaccination with this product
 - Local reactions: injection site pain, redness, and injection site swelling
 - Systemic reactions: pyrexia, vomiting, diarrhoea, headache, malaise, chills, myalgia, and arthralgia

8.2.3.3.1. Local reactions

Local reactions of maximum severity (by local reaction, any local reaction) will be summarized in terms of n and proportion (by severity, any severity). Local reactions of each severity and any severity will be summarized by time of onset (Day of vaccination, Day 2, Day 3, Day 4, Day 5, Day 6, Day 7) in terms of n and proportion, and figures corresponding to the tabulation of local reactions of each severity will be

prepared. In addition, summary statistics will be calculated by time of onset of each local reaction and any local reaction and the duration of each local reaction (date of resolution – first date of onset).

8.2.3.3.2. Systemic reactions

Systemic reactions of maximum severity (by systemic reaction, any systemic reaction) will be summarized in terms of n and proportion (by severity, any severity). Local reactions of each severity and any severity will be summarized by time of onset (Day of vaccination, Day 2, Day 3, Day 4, Day 5, Day 6, Day 7) in terms of n and proportion, and figures corresponding to the tabulation of local reactions of each severity will be prepared. In addition, summary statistics will be calculated by time of onset of each systemic reaction and any systemic reaction and the duration of each systemic reaction (date of resolution – first date of onset).

8.2.3.3.3. Occurrence of reactogenicity events in participants excluded from the safety analysis set

Using data from CRF-collected participants, reactogenicity events reported in participants excluded from the safety analysis set will be identified and presented in a tabular form. In addition, local reactions of maximum severity (by local reaction, any local reaction) will be summarized in terms of n and proportion (by severity, any severity). Systemic reactions will be summarized in the same manner.

8.2.3.4. Information about COVID-19

Using the safety analysis set, participants underwent or not underwent any COVID-19 pathogen test (nucleic acid detection test [PCR/LAMP], antigen test) will be summarized. Among participants underwent nucleic acid detection test or antigen test, those with each result (positive or negative) will be summarized in terms of n and proportion. Furthermore, positive participants will be summarized by kind of test in terms of n and proportion, and positive participants developing COVID-19 will be summarized by n and proportion. In addition, participants with severe COVID-19 will be summarized in terms of n and proportion (denominator = the number of participants with COVID-19) with severe cases being defined as any of the following actions taken during the period from disease onset to the outcome date:

- Admission to the ICU
- Use of mechanical ventilation
- Use of ECMO

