7. RESEARCH QUESTION AND OBJECTIVES

To collect information on adverse events, reactogenicity events (local reactions and systemic reactions), and COVID-19 observed after the fourth vaccination with this product in children aged 6 months to 4 years (as of the date of the fourth vaccination with this product) who received their first booster immunization with this product (hereinafter, the fourth vaccination with this product) after the initial immunization under actual use, and to confirm its safety in the early stage.

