8.3.7. Information on COVID-19

The investigator will confirm the presence or absence of the onset of COVID-19 during the observation period and enter the information.

- Presence or absence of COVID-19 onset (“present” should be selected if there are symptoms, and “absent” if there are no symptoms)

If the onset of COVID-19 is “present,” the following information should also be entered.

- Date of diagnosis of COVID-19
- Presence or absence of actions/procedures taken (administration of COVID-19 treatment drugs*, hospitalization, oxygen administration, ICU admission, use of mechanical ventilation, use of ECMO)

*: Treatment drugs with an indication for use in SARS-CoV-2 infection

- Outcome (resolved/recovered, resolved with sequelae, death, not resolved, and unknown) and date of outcome

The outcome should be followed up as much as possible even after the end of the observation period.

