2.1. Study Objective

To collect information on adverse events, reactogenicity events (local reactions and systemic reactions), and COVID-19 that occur subsequent to the fourth vaccination with this product in children aged 6 months to 4 years who received the first booster immunization with this product (fourth vaccination with this product) after the initial immunization under actual use, and to confirm its safety in the early stage.

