2.2.7. Planned sample size and its rationale

60 participants will be collected as the participants to be included in the safety analysis set.

The target sample size (safety analysis set) was set to be 60 participants based on feasibility. If 60 participants can be collected, an adverse event that occurs with a true incidence of 3% can be observed in at least 1 participant with a probability of 83%, which would make it possible to understand trends in incidence of reactogenicity events.

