4. HYPOTHESES AND DECISION RULES

Because of the non-confirmatory nature of this study, no hypothesis tests will be performed.

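### SAP 8.2.3.4 ties its only COVID-19 onset count to a positive test, leaves that proportion's denominator unstated, and does not define the group used as the severe-case denominator

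*SAP*

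**What the plan says.** The objective in Protocol 7 begins "To collect information on adverse events, reactogenicity events (local reactions and systemic reactions), and COVID-19 observed after the fourth vaccination with this product", and SAP 2.1 repeats it in nearly the same words.

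Protocol 8.3.7 defines the onset item: "The investigator will confirm the presence or absence of the onset of COVID-19 during the observation period and enter the information". The item is coded by whether symptoms are present, and a date of diagnosis is entered if they are. No positive test is named as a condition. Pathogen testing is a separate item (Protocol 8.3.6 and a separate row of Table 1), and its details are entered only when a test was done.

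SAP 8.2.3.4 opens by naming the safety analysis set. It then plans, in order: tested or not; results among those tested; positives by kind of test; "positive participants developing COVID-19 will be summarized by n and proportion"; and severe COVID-19 (ICU admission, mechanical ventilation or ECMO) as n and proportion, with "denominator = the number of participants with COVID-19".

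Protocol 8.7.4 asks only for the number and proportion of participants in a severe condition.

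**The concern.** The onset item covers every participant, but the onset table covers only those with a positive test. A child whose COVID-19 was diagnosed without a test, or after a negative one, can be recorded in the CRF and still not be counted in the section written for COVID-19.

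Two further gaps follow in the same section. The onset proportion has no stated base, so two programmers could produce very different percentages from the same children. The severe-case proportion rests on a group whose size appears in no planned table. The severe-case line carries no test condition either. If its denominator were read as symptomatic positives, a severe case without a positive test would sit in the numerator but not in the denominator.

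At stake are the count for one named part of the objective and the base of the severe-case proportion. The latter bears on vaccine-associated enhanced disease, which both documents list as an important potential risk.

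**Working it through.** **The plan's own figure.** SAP 2.2.7 states "60 participants will be collected as the participants to be included in the safety analysis set" and gives an 83% chance of seeing at least one event of true incidence 3%. Check: 1 − 0.97^60 = 0.8392, or 83.9%. The figure reproduces (truncated rather than rounded). It supplies N = 60 but does not bear on which children are counted.

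**Do other sections fill the gap?**
- SAP 6.1 does not list COVID-19 onset as an endpoint, and SAP 6.3 (other endpoints) is not applicable.
- SAP 9 names no listing of COVID-19 cases or test results.
- SAP 8.2.3.2 tabulates serious and non-serious adverse events by SOC and PT, and SAP 9 lists all participants with adverse events. COVID-19 information in the diary can reach these through Protocol 8.3.8, but it is verified as needed, an incidence threshold may be applied to the non-serious table, and neither output uses the onset item.
- SAP 8.2.3.6 allows exploratory analyses, which are optional and reported selectively.

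**Size, by illustration.** The documents give no COVID-19 counts and no share tested, so the counts here are assumed: N = 60; 4 test-positive children, all symptomatic; 0 to 4 further children with onset present but no positive test; one severe case, itself test-positive. Intervals are exact (Clopper-Pearson), the method of SAP 8.1.3: lower limit = 2.5% quantile of Beta(x, n − x + 1), upper limit = 97.5% quantile of Beta(x + 1, n − x).

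Existing onset line, same 4 children, two possible bases:
- over positives: 4/4 = 100% (39.8% to 100%)
- over the safety analysis set: 4/60 = 6.7% (1.8% to 16.2%)

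All children with onset present, and the severe proportion over that group:

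| Cases without a positive test (assumed) | All cases over 60 | Exact 95% CI | One severe case over all cases |
|---|---|---|---|
| 0 | 4/60 = 6.7% | 1.8% to 16.2% | 1/4 = 25.0% |
| 1 | 5/60 = 8.3% | 2.8% to 18.4% | 1/5 = 20.0% |
| 2 | 6/60 = 10.0% | 3.8% to 20.5% | 1/6 = 16.7% |
| 4 | 8/60 = 13.3% | 5.9% to 24.6% | 1/8 = 12.5% |

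If the severe denominator were read as symptomatic positives, the last column would stay at 25.0% in every row. The gap between 100% and 6.7% comes only from the unstated base. The move from 6.7% to 13.3% comes only from cases outside the test-positive count.

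**The case against.** A reader might infer that the SAP never gives COVID-19 occurrence in the safety analysis set. The text does not support that. The base of the onset proportion is unstated, not fixed as positives. The section opens with the safety analysis set and names a narrower base in two other places, so n over the safety analysis set is a fair reading. A reader could also divide the reported n by the size of the set. Either route gives a figure for test-positive cases only.

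A reader might also infer that clinically diagnosed cases are lost. That too goes beyond the text. They may enter the severe-case denominator, which has no test condition, and they may appear in the adverse event tables and in the adverse event listing, which has no threshold. What stands is that they are outside the dedicated onset count and that the other routes are not certain to hold each case.

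The onset item might itself be meant to separate symptomatic from asymptomatic infection. Protocol 8.3.1 uses the same coding for past infection, and there it is asked only when infection is present. Protocol 8.3.7 does not state that condition, and neither place requires a recorded positive test, so this narrows the point without removing it.

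Finally, the objective is to collect information, "no hypothesis tests will be performed", there is no effectiveness endpoint, and Protocol 8.7.4 prescribes only severe-case counts. The SAP therefore omits no table that the protocol required. This stands in full: the gap is against the objective and the data collected, not against a protocol-specified analysis.

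**Conclusion.** The point holds as a gap in specification. The only planned onset count is limited to test-positive participants, its proportion has no stated base, and the severe-case denominator is a group that is neither tabulated nor defined in relation to that count. The onset count can understate recorded cases but cannot overstate them.

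The size cannot be determined from the documents. Under the assumed 4 symptomatic positives in 60, the total runs from 6.7% (no cases without a positive test, so no undercount) to 13.3% (four such cases). The severe proportion with one test-positive severe case runs from 25.0% down to 12.5%. These are illustrations, not estimates, and the true effect may be zero. The conclusion assumes that onset can be entered as present without a recorded positive test, which Protocol 8.3.7 permits as written.

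**What to change.** In SAP 8.2.3.4:

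1. Add the n and proportion, with exact 95% CI, of all participants with COVID-19 onset recorded as present, over the safety analysis set, split into test positive, test negative and not tested. Because each test is recorded separately, say how a child with several results is classified, so that the rows do not overlap.
2. Define the denominator for severe COVID-19 as this total.
3. State the denominator of the existing test-positive onset proportion.

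The cost is a wording change and a few table rows from data the CRF already holds. The downside is that the total will include cases without laboratory confirmation; the split shows them separately, so a reader can still take the test-positive figure alone.
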